11.0 RESEARCH STAFF TRAINING

Research staff will be trained as specified in the Study Training Plan developed by the Lead Node, the CCC, the DSC, and other members of the Lead Team. Additional details and guidance for study procedures will be provided in a Manual of Operating Procedures (MOP) and in local SOPs. Research staff training will be conducted via in-person training sessions, webinar presentations, and/or telephone conferences. Required training will include Human Subjects Protection (HSP) and Good Clinical Practice (GCP), as well as protocol-specific training as needed (e.g., assessments, safety procedures, data management and collection). Research staff collecting and entering data in Advantage eClinical will complete training on electronic case report form (eCRF) data entry, data management and integrity, and the Advantage eClinical data system. In-person practicums will be required of study staff conducting the recruitment, Informed Consent, urine drug screening, and the TLFB. All study staff will be required to complete the study-specific training plan for their assigned study role as well as satisfy any training requirements per local institutions.

12.0 STATISTICAL DESIGN AND ANALYSES

12.1 General Design

CTN-0079-A1 is an implementation study that will use mixed methods and triangulate multiple sources of data collected over the course of the parent (CTN-0079) and the ancillary studies to evaluate the feasibility, acceptability, sustainability, and impact of the ED-initiated BUP clinical program and implementation facilitation strategy and identify factors influencing diffusion and effectiveness. The ancillary study involves three phases of participation: 1) candidates for ED-initiated BUP enrolled over a 12-month period (Post-IF and Maintenance periods, 6 months each) to participate in two research visits (Days 0 and 30) and/or authorize administrative data matching, 2) ED staff, patients, and stakeholders' participating in semi-structured qualitative interviews/focus groups at study close, and 3) retrospective chart review and data matching for all adult ED patients identified to have non-medical opioid use presenting to the ED during the IF, Post-IF or Maintenance periods.

12.2 Recruitment and Enrollment

The ancillary study participants are planned to be identified from parent study sites: Catholic Medical Center, Valley Regional Hospital, and Bellevue/NYC Health and Hospitals. The study population will consist of ED patients who are candidates for ED-initiated BUP. We anticipate that, 300 ED patients (150 identified during each ancillary study period) will be found that meet this criterion. This is the population for evaluating the primary and key secondary implementation outcomes. Of those patients, approximately 120 (i.e., 120/300=40%, with 60 participants enrolled during each ancillary study period) will enroll as Full Study patient-participants. This is the population for evaluating the primary and key secondary effectiveness outcomes. We also anticipate that as many as an additional 180 patient-participants will enroll in the Limited Study and have included an additional 20 Limited Study patient-participants in case this number is higher than anticipated for a total N=300 (120 + 180 + 20) for data matching outcomes. Based on data from parent study, we approximate 40% to 90% of ED patients that are eligible for and willing to receive ED-initiated BUP will actually receive it, and 40% to 80% of enrolled patient participants will be engaged in formal treatment within 30 days following ED discharge. Table 4 shows the expected cumulative number of individuals identified and those anticipated to receive ED-initiated/expedited BUP for primary implementation outcome, as well as the number of individuals enrolled and engaged in formal treatment for primary effectiveness outcome. We present the number of expected ED-initiated/expedited BUP receivers and those engaged to formal treatment for the lowest and highest success rates (i.e., 40% and 90% for primary implementation outcome, and 40% and 80% for primary effectiveness outcome).

z	Phase	Primary Implementation Outcome N=300			Primary Effectiveness Outcome N=120		
		Number identified	Number who received ED-initiated/expedited BUP assuming, 40% - 90% success rates		Number enrolled	Number engaged in formal addiction treatment for OUD, assuming 40% - 80% success rates	
			40%	90%		40%	80%
Post-IF Period							
1		25	10	23	10	4	8
2		50	20	45	20	8	16
3		75	30	68	30	12	24
4		100	40	90	40	16	32
5		125	50	113	50	20	40
6		150	60	135	60	24	48
Maintenance Period							
1		175	70	158	70	28	56
2		200	80	180	80	32	64
3		225	90	203	90	36	72
4		250	100	225	100	40	80
5		275	110	248	110	44	88
6		300	120	270	120	48	96

Table 4: Expected cumulative numbers of individuals capable of being assessed for selected study milestones outcomes across Post-IF and Maintenance Periods by month

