Patients who receive ED-initiated BUP during times without research staff coverage will be contacted for potential study participation as soon as possible following ED discharge. Candidates who do not receive BUP will not be contacted once they have left hospital premises. As in the parent study, research staff will utilize available contact information, including information provided at registration or documented in the EMR, to contact candidates, assess eligibility, and offer study participation. Each site's clinical protocol includes a procedure to notify ED patients that clinical or research staff may contact them for follow up purposes and/or to discuss participation in a research study. Patients may opt out of contact from research staff. Assessment of study eligibility will be conducted by trained research staff and may be completed by phone or in person (upon return). Candidates who are determined to be eligible for and interested in study participation will be scheduled for written consent and baseline assessments to be completed in person, ideally within 72 hours of ED discharge but recruitment efforts may continue for up to 7 days post ED discharge.

It is anticipated that some patients will be difficult to reach due to insufficient contact information, homelessness, admission to a treatment program, or other reasons. Of the patients reached, it is expected that some may choose not to participate and that some patients may fail to present for the baseline visit within the visit window. Research staff will make repeated attempts (at varying times of the day- morning, afternoon, evening) to contact all candidates utilizing multiple methods of communication (i.e., call, text, email). Research staff will also strive to reduce barriers to participation by offering to complete the visit at a time and location that is convenient for the participant. All candidates will be informed that they will receive compensation for participation.

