We will strive to keep recruitment relatively even across all sites through purposive sampling and employing a recruitment strategy, defined in the MOP, that includes enrollment rate limits based on the relative number of participants enrolled at each site. As our effectiveness outcomes focus primarily on recipients of ED-initiated BUP, we will also employ a recruitment strategy that preferentially enrolls patients receiving ED-initiated BUP to those not receiving ED-initiated BUP. Similarly, we will preferentially enroll females as they are known to be underrepresented.

9.4.1.2 *Informed Consent*

Patients endorsing non-medical opioid use on the ED Health Survey and who are not currently taking prescription opioids or MOUD, will be asked to provide verbal consent to complete screening procedures. After the individual has provided verbal (not signed) consent, research staff will complete the DSM-5 checklist for OUD, demographic information, and confirm that the candidate meets all the inclusion criteria and none of the exclusion criteria. Candidates who meet all eligibility criteria will be offered participation. Reasons for exclusion or non-participation will be documented. Candidates who do not meet eligibility for the Full Study, will be assessed for participation in the Limited Study (section 10.15).

All candidates remaining eligible following this study screening will be asked to provide written informed consent to participate in both data matching and research assessments using the IRB-approved informed consent document. Prior to documenting written informed consent, research staff will explain the study to the potential participant and provide a copy of the consent to read and reference during the consent discussion. All candidates will receive a verbal explanation in terms suited to their comprehension of the purposes, procedures, and potential risks of the study and their rights as research participants. A discussion of risks and possible benefits will take place with the participants. Candidates will have the opportunity to carefully review the written consent form and ask questions prior to signing. If the candidate is interested in participating in the study, a research staff member will review each section of the IRB-approved informed consent form in detail and answer any questions the participant may pose.

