12.3.2 Definition of Primary Effectiveness Outcome

The primary effectiveness outcome measure is engagement in formal addiction treatment for OUD on the 30th day following ED discharge. The primary effectiveness outcome is defined as: the proportion of participants who are confirmed to be engaged in formal addiction treatment for OUD on the 30th day following ED discharge, amongst participants who received ED-initiated/expedited BUP. The outcome will be calculated as a pooled success rate over Post-IF and Maintenance periods.

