12.3.3.2 Secondary Effectiveness Outcome Measures

The key secondary effectiveness outcome is linkage to formal addiction treatment for OUD within one week (operationalized at within 7-10 days). This is a binary outcome and will be defined as the proportion of participants with (objectively) confirmed linkage to formal addiction treatment for OUD within one week following ED discharge, amongst participants who received ED-initiated/expedited BUP. The outcome will be calculated as a pooled success rate over Post-IF and Maintenance periods.

Other secondary effectiveness analyses will evaluate the participant subgroups who received ED-initiated BUP and ED-expedited BUP separately as well as those who did not receive BUP.

As in the parent study, a range of secondary effectiveness measures will be assessed at the index ED and Day 30 visits, including but not limited to:

- Self-reported days of opioid and other drug use (TLFB)
- UDS results at 30 days post index ED visit
- Overdose events
- Healthcare utilization
- Quality of Life, Health, and Treatment Effectiveness (PROMIS-29, PHQ-9, TEA)
- Treatment satisfaction and acceptability

Process measures related to the clinical protocol include but are not limited to:

- Proportion of ED patients triaged who are screened for non-medical opioid use
- Proportion of those screened who are positive for non-medical opioid use
- Among those positive:

- Proportion who are candidates to receive ED-initiated BUP
- Proportion who receive ED-initiated BUP (and whether via direct administration, prescription, and/or warm referral within 24 hours)
- Numbers meeting inclusion/exclusion criteria for ED-initiated BUP
 - DSM-5 moderate-to-severe OUD
 - Use opioids in past 7 days
 - Not engaged in medication treatment for OUD
- Proportion who received facilitated referral for treatment amongst those who received some form of ED-initiated BUP.
- Fidelity
 - Critical actions completed

Implementation barriers and facilitators, include:

- Stakeholder acceptability over time (key informant interviews, focus groups)
- ED staff, patient, community barriers and facilitators (key informant interviews, focus groups)

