12.5 Precision Analyses for Primary Outcomes

We assume that 300 ED patients (150 at each ancillary study period) identified uniformly across the 3 sites will be found to be candidates for ED-initiated BUP. This is the population for the denominator of the primary implementation outcome. We also assume that, of these, approximately 120 participants will get enrolled in the Full Study and become available to evaluate the effectiveness primary outcome. Based on previous assumptions, and data from the parent study, we assume that the true proportion (success rate) of these individuals that actually receive ED-initiated BUP is between 40% to 90%, and the true proportion (success rate) of participants who were engaged in formal addiction treatment for OUD on the 30th day following ED discharge is between 40% to 80%.

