12.5.3 Summary of Precision Analyses

For all the simulation scenarios investigated for primary implementation and effectiveness outcomes, the 90th percentiles of the 95% confidence interval widths seem to decrease with increase in site differences and are relatively lower for larger sample size; the planned sample sizes of $N=300$ (ED patients) and $N=120$ (participants), but are all below 0.2 and 0.3 for implementation and effectiveness probabilities, respectively. This means for each scenario investigated, 90% of the confidence interval widths are less than 0.2 and 0.3, respectively. The narrow confidence widths imply that, the estimated success rates are good representatives of the true implementation and effectiveness probabilities. There is minor downward bias that seems to diminish with increase in site differences for the implementation probability and effectiveness probability, but the bias is minimal for all the scenarios investigated. In summary, for the planned sample sizes, and for all scenarios investigated, the estimates for the primary implementation and effectiveness outcomes have small bias and capture the true outcomes with high precision.

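### The effectiveness sample size counts all 120 or so Full Study enrollees, but the outcome is defined only for those who received buprenorphine, and no expected number of these is given

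*Combined protocol and SAP*

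**What the plan says.** **Planning text.** Section 12.2 expects 300 candidates and states: "Of those patients, approximately 120 (i.e., 120/300=40%, with 60 participants enrolled during each ancillary study period) will enroll as Full Study patient-participants". It continues: "This is the population for evaluating the primary and key secondary effectiveness outcomes". It assumes that 40% to 80% of enrolled participants will be engaged in treatment. Table 4 heads its effectiveness block N=120, applies 40% and 80% to the number enrolled, and ends at 48 and 96 engaged. Section 12.5 assumes that "approximately 120 participants will get enrolled in the Full Study and become available to evaluate the effectiveness primary outcome". Section 12.5.1 simulates N=60, 90 and 120. Section 12.5.3 reports 90th-percentile interval widths below 0.3 for effectiveness and concludes that "for the planned sample sizes, and for all scenarios investigated, the estimates for the primary implementation and effectiveness outcomes have small bias".

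**Outcome definition.** Section 12.3.2 takes the primary effectiveness proportion "amongst participants who received ED-initiated/expedited BUP". Section 12.3.3.2 uses the same denominator for linkage, and sections 2.3, 4.1.1 and 8.1.2 agree.

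**Who can enrol.** Section 7.2.1 requires candidacy, by clinical or research determination, and not receipt. Section 12.3.3.2 plans to "evaluate the participant subgroups who received ED-initiated BUP and ED-expedited BUP separately as well as those who did not receive BUP". Section 9.4.1.1 describes a strategy that "preferentially enrolls patients receiving ED-initiated BUP to those not receiving ED-initiated BUP" and adds: "Candidates who do not receive BUP will not be contacted once they have left hospital premises". Neither statement comes with a number, a share or a target.

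**The concern.** The sample-size text and the outcome definition use different denominators. They coincide only if no non-recipient enrols, which would leave the planned non-recipient subgroup empty.

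The primary analyses are descriptive (section 12.4), with no hypothesis test or power target. Precision is therefore the only justification offered for the effectiveness sample size, and it should be quoted at the number that will be analysed. Table 4's engaged counts are affected in the same way, as is the base to which the 40% to 80% engagement assumption is attached.

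**Working it through.** **1. Reproduce the plan's figures.** Table 4, last row: 120 × 0.40 = 48 and 120 × 0.80 = 96, which match. The base is therefore all enrollees.

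For precision, we re-implemented the estimator in section 12.5.1. Each site has a Beta(S+1, F+1) mean and variance. The overall estimate is the average of the three site means, its variance is the sum of the site variances divided by 9, and the limits are ±1.96 standard errors, clipped to 0–1. With equal sites, no site difference and p from 0.4 to 0.8, the largest 90th-percentile widths were 0.235 (N=60), 0.196 (N=90) and 0.172 (N=120). All are below 0.3, as the plan states. The scale of the site-variability parameter is not defined in the text. Read as a shift on the logit scale, larger values narrowed the intervals, so zero is the conservative case.

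**2. What a denominator of 120 would require.** Inputs from section 12.2: 300 candidates, receipt rate r of 40% to 90%, 120 enrollees. The 65% rate is our midpoint. With no non-recipient enrolled, the share of recipients who must enrol is 120/(300 × r):

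- r = 0.40: 120/120 = 100%
- r = 0.65: 120/195 = 62%
- r = 0.90: 120/270 = 44%

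The plan expects 120/300 = 40% of candidates overall to enrol.

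**3. Recipients among 120 enrollees.** Let recipients be k times as likely to enrol as non-recipients, with enrolment fixed at 120. Then N = 120 × r × k / (r × k + 1 − r). The documents give no k, so 1, 2 and 3 are our assumptions. Example for r = 0.40, k = 2: 120 × 0.8/(0.8 + 0.6) = 69.

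| k | r = 40% | r = 65% | r = 90% |
|---|---|---|---|
| 1 | 48 | 78 | 108 |
| 2 | 69 | 95 | 114 |
| 3 | 80 | 102 | 116 |

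**4. Consequences at each N.** Engaged is 0.4 × N to 0.8 × N. Width is the 90th percentile at p = 0.5 (the widest case), with equal or near-equal sites, no site difference and 200,000 iterations.

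| N | Engaged | Width |
|---|---|---|
| 48 | 19–38 | 0.259 |
| 69 | 28–55 | 0.221 |
| 78 | 31–62 | 0.209 |
| 80 | 32–64 | 0.207 |
| 95 | 38–76 | 0.192 |
| 102 | 41–82 | 0.186 |
| 108 | 43–86 | 0.181 |
| 114 | 46–91 | 0.176 |
| 116 | 46–93 | 0.175 |
| 120 (plan) | 48–96 | 0.172 |

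**5. Bias.** With n participants per site, the estimator's bias is (1 − 2p)/(n + 2). At p = 0.8 this is −0.6/42 = −0.014 for N=120, −0.6/28.7 = −0.021 for N=80 and −0.6/18 = −0.033 for N=48. It is zero at p = 0.5 for every N; p = 0.8 is the edge of the plan's range, where it is largest.

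**6. Uneven sites.** Section 9.4.1.1 seeks even enrolment across sites, but receipt may still differ between them. At N=48 and p = 0.5 the width is 0.262 for a 20/16/12 split and 0.270 for 24/14/10. More extreme splits give about 0.30 (30/12/6) and 0.33 (36/8/4). All four splits are illustrations.

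**The case against.** The strongest reply is that nothing the plan concludes is overturned. The bound of 0.3 was checked at N=60 and N=90 as well as 120, which corresponds to recipient shares of 50% and 75%. With equal sites the bound holds down to about N=33. That stands, although section 12.5.1 does not tie the smaller runs to recipient share.

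Second, N=48 needs both the lowest receipt rate and no enrolment preference, whereas section 9.4.1.1 prefers recipients and rules out contacting non-recipients who have left. That also stands: 48 is likely pessimistic, and with k of 2 or 3 every N lies between 69 and 116, inside the simulated range. Two cautions remain. The stated preference names ED-initiated buprenorphine only, so it may not extend to expedited recipients. And a preference is not an exclusion.

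Third, the outcome definition is consistent throughout, so an analyst would use the right denominator. Loss to follow-up counts as failure (section 12.10), so the number does not shrink further. The monitoring plan in Appendix A already reports the number of enrolled participants receiving buprenorphine. These points limit the harm. But without an expected value, that monitored count has nothing to be compared with.

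Finally, Table 4's multiplication is correct. The fault is the base to which it is applied, not the arithmetic.

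**Conclusion.** The concern holds. Section 12.2, section 12.5 and Table 4 size the effectiveness outcomes on all enrollees, while the definitions restrict them to recipients, and no expected number of enrolled recipients appears anywhere.

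The size depends on how strongly recruitment favours recipients, which the documents do not quantify. Over the assumed range, the denominator runs from 48 to 116 and the width from 0.259 to 0.175, against 0.172 at 120. The worst case is about 50% wider (0.259/0.172 = 1.51); the best is nearly unchanged. The bound of 0.3 survives with equal or mildly uneven sites, and fails only if about 48 recipients fall very unevenly across sites.

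The error is confined to planning figures: the definition and analysis method are unaffected. It should be fixed because these figures are the only support for the sample size of a primary outcome.

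**What to change.** - In sections 12.2, 12.5 and 12.5.3, label 120 as Full Study enrolment. State the expected number of enrolled participants who received ED-initiated or ED-expedited buprenorphine, with a range and the assumed effect of preferential enrolment. Name them as the population for the primary and key secondary effectiveness outcomes.
- State whether the 40% to 80% engagement assumption refers to recipients.
- In Table 4, keep the number enrolled, add the number enrolled who received buprenorphine, and apply 40% and 80% to the latter.
- Quote width and bias at the expected recipient number. If the range lies within 60 to 120, the existing runs bracket it for equal sites. If it goes lower, re-run the existing code below 60. Add some unequal site splits in either case.

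The cost is wording, three Table 4 columns and a re-run of existing code. Eligibility, outcome definitions and clinical care do not change. The stated precision becomes somewhat less favourable.

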12.3 Primary and Secondary Outcomes Measures

12.3.1 Definition of Primary Implementation Outcome

The primary implementation outcome measure is receipt of ED-initiated/expedited BUP. This is a binary outcome and will be defined as the proportion of ED patients receiving ED-initiated/expedited BUP amongst ED patients who are candidates for ED-initiated BUP. Receipt of ED-initiated/expedited BUP will be operationally defined to include: (1) administration of BUP in the ED, (2) prescription for BUP as part of the ED visit, or (3) provision of a specific “warm” referral or transfer of care to a provider, clinic, or treatment setting with the capacity to administer or prescribe BUP within no more than 24 hours. Data for implementation primary outcome will be abstracted from the health record (EMR abstraction) and/or determined through research staff assessments. The outcome will be calculated as a pooled success rate over Post-IF and Maintenance periods.

12.3.2 Definition of Primary Effectiveness Outcome

The primary effectiveness outcome measure is engagement in formal addiction treatment for OUD on the 30th day following ED discharge. The primary effectiveness outcome is defined as: the proportion of participants who are confirmed to be engaged in formal addiction treatment for OUD on the 30th day following ED discharge, amongst participants who received ED-initiated/expedited BUP. The outcome will be calculated as a pooled success rate over Post-IF and Maintenance periods.

